## **X. CONSENT PROCESS**

---

When a participant arrives for their Baseline Appointment (Session 1) at the Center for Innovation and Creativity (CINC), a member of the research team will greet him or her in the first-floor lobby. The research assistant will take the participant to a private room and provide the participant with a copy of the informed consent document. Prior to asking the participant to sign the consent form, the trained research assistant and the participant will have a discussion regarding the research study. Additionally, the research assistant will be available to answer any questions he or she may have about the study. We will also explain that participation includes an appointment in our Mobile Van Pharmacology and Phlebotomy Laboratory (4-Week Appointment), which will be seen outside their home, possibly by their neighbors, and that privacy may not be maintained. Participation will be clearly stated as voluntary, with the option to withdraw at any time. There will be no deception involved with this study. After discussing the study and going over the consent form with the researcher, the participant will be included in the study if they choose to initial and sign the informed consent document.

## **XI. PROCESS TO DOCUMENT CONSENT IN WRITING**

---

In accordance with 45 CFR 46.117, a printed copy of the written informed consent document will be signed by the participant, and an unsigned copy of the form used to document consent will also be given to the study participant electronically.

## **XII. PROCEDURES**

---

Participants will contact the researchers with their interest by phone, e-mail, or through an online screening survey (RedCap, provided as a CCTSI resource). In the case that a potential participant requests more information via e-mail or voicemail message, the research assistant responding to the message will ask the participant to call the lab phone number for more information (same phone number provided on all study advertisements), e-mail the study team a phone number at which the potential participant could be reached at and a desirable time for the research staff to call, or to complete the online survey. The first page of the online screening

survey will give a brief description and the estimated time involved in completing the screening process and the study (in the case that they are eligible and elect to participate) and instructed to click the *Next Page* button if they wish to be screened further. The online screening that follows will be identical to the phone screening. All subjects that complete the screening will be asked to leave their preferred contact information and the best time to contact them so that a research assistant can inform them of eligibility (according to the inclusion/exclusion criteria list in Section VI above) and answer any questions they may have. For participants that prefer to complete a phone screening, a trained research assistant will provide an overview of the study, answer any questions that the potential participant has, and then screen them for preliminary eligibility according to the inclusion/exclusion criteria list in Section IV above. This process will help to ensure participants have ample opportunity to be informed of the main study components and maintain their privacy as much as possible. If the participant meets the study criteria after the initial online screening survey or phone interview and the follow-up contact, they will be invited to come to the CU Change Laboratory at the CINC for their Baseline Appointment. If any subject is questionable for inclusion, our PI ([name], a licensed clinical psychologist) and Co-I team will make the final determination of eligibility.

**COVID-19:** Before interacting with research assistants, eligible participants will be asked additional questions related to COVID-19. These questions will be administered prior to any in-person appointment and by a research assistant over the phone (or at a distance of at least 6-feet if the participant is unable to complete the questions over the phone). These questions will be administered to protect staff and participants from the spread of COVID-19. The questions are a precaution based on current university and Centers for Disease Control and Prevention guidelines and may need to be updated as the understanding of COVID-19 evolves. These procedural questions are temporary in nature and will be lifted once university guidelines deem it unnecessary.

**Baseline Appointment (Session 1) Procedures.** Subjects who meet inclusion criteria will be scheduled for a Baseline Appointment and given instructions for the assessments, including not consuming alcohol or marijuana for 24 hours, or caffeine for 4 hours prior to coming into the lab for their sessions. After arriving at the CUChange Lab, each subject will go through the consent process and be breathalyzed to ensure a breath alcohol concentration of zero. A urine toxicology screen (and a pregnancy test for females) will also be administered to insure that subjects have not recently taken illicit drugs (and are not pregnant). Menstrual cycles and birth control use will be reported. A baseline blood draw (see details below) will be taken to quantify inflammatory biomarkers and cannabinoids. A member of our research team who has completed a certified training in phlebotomy will collect a blood sample. All blood draw procedures performed during this study will involve collecting venous blood (40 ml total/session) venipuncture of a peripheral arm vein using standard, sterile phlebotomy techniques. Subjects will then be administered the Beck Anxiety Inventory (BAI), the State Trait Anxiety Inventory (STAI), the Depression, Anxiety, and Stress Scale (DASS), and complete measures related to alcohol/drug use history, mood, stress, and quality of life and will complete cognitive testing (see Table 2 below for measures to be completed).

After completing the final blood draw, subjects will receive training in the use of online daily assessments (see details below) and the three user groups will then be assigned a marijuana strain to use for the next four weeks instead of their typical strain. Marijuana using participants will be

randomly assigned to one of three marijuana strains (a THC-based strain akin to a typically used strain with normal levels of THC and little to no CBD, a THC and CBD strain in combination, with a 1:1 ratio between THC and CBD levels, or a CBD-enriched strain with little to no THC, and then given instructions to purchase their assigned strain (labeled either C, D, or E) at a good clinical practice local dispensary. Marijuana users will be asked to use their assigned strain (and only that strain) as they wish over the course of the next four weeks. Non-users will be asked to continue to abstain from marijuana use over the next four weeks. After completing the measures and procedures, research study staff will answer any questions subjects have on their daily messages (see details below), debrief participants, and compensate them with \$80 in cash for their time and effort during the Baseline Appointment. Lastly, each participant will be scheduled for their 2-Week (Session 2) Apppintment at the CINC for two-weeks later.

**Blood Levels of Inflammation.** As noted in the background and in our description of our preliminary studies, we expect that CBD and THC will reduce biomarkers related to inflammation during the course of the study. Blood samples drawn at each Session will be assayed for IFNg, IL-1a, IL-1b, IL-6, IL-2, IL-4, IL-8, IL-10, IL-12, and TNF. Previous studies in animals (Mayfield et al., 2013) and humans (Bala et al., 2014), as well as our own preliminary data, suggest that cytokine activation is associated with the pathophysiology of anxiety disorders. This is the same assay used in our preliminary studies. We also expect CBD and THC to impact the responses of blood monocyte cells to a lipopolysaccharide (LPS) challenge (see details below). This may represent a more accurate test of the effects of the CBD and THC, since LPS stimulation of peripheral blood mononuclear cells (PBMCs) simulates the inflammation cascade that putatively mediates the neuroinflammatory effects of pain. To that end, 40 mL of whole blood will be drawn at each session (1-4). We will use 22 ml of blood to perform the inflammatory analysis, 10 ml of that blood for DNA extraction, and 8 ml of blood for cannabinoid analysis. There will be four blood draws total, with one during the Baseline Appointment (Session 1), one during the 2-Week Appointment (Session 2) and two during the 4-Week Appointment (Session 3 & 4 in the Mobile Van), separated by ~15 min (flower users) to one hour (edible users) for appropriate absorption. We will measure changes in cannabinoid and inflammatory levels after the long (2- and 4-week pre) and short/acute (4-week post) time course of cannabis consumption.

**DNA collection.** DNA will be extracted from 10 ml of blood (out of the total 40 ml collected) at each visit. After extraction, DNA will be quantified and stored at -80° for future analysis. DNA will be collected to look at differences in epigenetic and single nucleotide polymorphisms (SNPs) in participants with varying levels of cannabinoid content after choosing to use cannabis with high versus low THC and CBD content. The blood DNA samples collected in this study are primarily for bio-banking purposes at this time, as the analysis of these samples are expected to be performed at a future date and therefore may contribute to the current study and/or future studies.

**Lipopolysaccharide (LPS)-PBMC challenge.** Cannabis has been shown to mediate the pro-inflammatory effects of LPS, therefore, this LPS challenge may represent an accurate test of the effects of the CBD and THC, as LPS stimulation of peripheral blood mononuclear cells (PBMCs) simulates the inflammation cascade that putatively mediates the neuroinflammatory effects of anxiety. To that end, PBMCs will be separated using density gradient centrifugation. Cells will be counted and viability assessed using trypan blue exclusion. PBMCs will be exposed to LPS (0, 0.1, 1, 10 and 100 ng/ml) for 20h in a 96 well v-bottom plate. Protein levels of

cytokines and chemokines (IFNg, IL-1a, IL-1b, IL-6, IL-2, IL-4, IL-8, IL-10, IL-12, and TNF) will be measured in supernatant using a multiplex ELISA assay (Aushon Biosystems, Billerica MA). Messenger RNA (mRNA) levels of the same cytokines and chemokines will be measured in cell lysates using real-time PCR. We have successfully performed the PMBC isolation and LPS challenge in other projects.

**Gut Microbiome Sample Collection.** Participants will be instructed on how to collect and return microbiome samples at the Baseline Appointment. Gut flora (from fecal samples) will be collected from participants using at-home kits and then stored at -80°. Subjects will be given one kit during their 2-Week Appointment and will return the kit to research staff at their 4-Week Mobile Lab Appointment (in the Mobile Van). A short dietary survey (EATS) will be conducted at the 2-Week and 4-Week Pre-administration Appointment to complement the microbiome kit and blood data collected. The microbial DNA collected in this study are primarily for bio-banking purposes at this time, as the analysis of these samples are expected to be performed at a future date and therefore may contribute to the current study and/or future studies.

We expect to see changes in abundance and diversity of microbiota populations found in the gut as a result of cannabis use. Because substance use, inflammation, and the gut microbiome, as well as pain and anxiety, and inflammation and the gut microbiome are all heavily intertwined (Fung et al 2017, Gorky & Schwaber 2016, Leclercq et al 2014, Mayer et al 2015, Peterson et al 2017), we will examine the relationship between changes in the gut microbiome with changes in anxiety and inflammatory biomarkers in the blood (cytokines and blood monocyte cell response to LPS challenge) as a result of cannabis use. Microbial DNA will be extracted from fecal samples and then analyzed to determine how many and which bacterial species are present in the gut. Gut microbiome data will be collected at two time-points during this study, once before and one after study cannabis use (i.e., with assigned cannabis ratios).

**Daily (Online-based message) follow-up Assessments.** Ecological momentary assessment of marijuana use via messaging has been shown to be feasible in a variety of marijuana users. During the 4 week study, marijuana users will answer online survey assessments via email with individually tailored links hosted by our university's licensed survey tool RedCap. During the 4-Week study period, participants will report *daily* on the anxiety, their marijuana use, other stress management strategies, and their sleep pattern. This brief message report will provide a daily repeated measure of our primary constructs (anxiety and marijuana use) and potential mediators or moderators over the course of the 4-Week study. All subjects will be given extensive instructions on completing the daily message at the Baseline Appointment and will practice answering the questions in the lab using their cell phone or a lab computer to ensure they understand the process and time commitment. To enhance the response rate, participation on daily message follow-ups will be monitored and participants will be contacted if they do not respond for two consecutive days of daily messages. Participants will then be compensated for their time and effort during the 2-Week and 4-Week Appointments, receiving a \$1/day with a \$5 bonus for completing 13 of 15 online follow up message reports for each two-week period (\$40 in total possible).

**2-Week Appointment (Session 2) & 4-Week Appointment (Sessions 3 & 4).** All procedures in the baseline assessment (blood draws for cannabinoids and inflammation markers, anxiety and health self-report measures, cognitive testing, as well as past two week measures of health behavior and substance use will be completed two weeks after the baseline session (Session 2) and finally at four weeks after the baseline session (Sessions 3 & 4).

The 2-Week Appointment (Session 2) will take place at our lab in the CINC and includes all session 1 measures; peripheral inflammation, and cannabinoid levels. However, we will not conduct the Rumination Induction task, but will add the Patient Global Impression of Change scale (Guy, 1976), which asks participants to rate their improvement over the prior two weeks on a 7-point scale. Subjects will also be given one at-home microbiome collection kit at this visit with instructions on completing and returning the completed kit as near as possible to their 4-Week Appointment (after using their product). Participants will be given an ActiGraph wearable device as well on this Appointment, to use to track their physical activity and sleep during the final 2-Week study period (<http://actigraphcorp.com/>). They will be instructed on how to wear and use the device at this 2-Week Appointment. Participants will be instructed to wear the device as long as they feel comfortable during the last 2-4 Week period and to return the device at the 4-Week Mobile Appointment (3rd Appointment). Up to three attempts will be made to contact the participant and collect any wearable watch device that is not recovered (for any reason). The research staff will not make further attempts to collect the device, and will consider the device forfeited and irretrievable after this point. At the end of the 2-Week Appointment, research study staff will debrief participants and compensate them with up to \$80 (\$60 for the 2-Week visit and an additional \$20 for the first 15 or 30 daily message reports) in cash.

For the 4-Week Appointment (Sessions 3 & 4), we will travel to the participant in our Mobile lab in order to ease subject burden and to get a more accurate measurement of acute cannabis effects. We will collect the microbiome kit. We will also complete the Rumination Induction Exercise for the 2nd and 3rd time (pre and post-cannabis use), and measure stress induction (via the Visual Analog Scale 1-100) both before and after Rumination Induction. We will also complete two new surveys (Drugs Effect Questionnaire and Addiction Research Center Inventory) to document the current effects and feelings that the subject has before and after cannabis use. After completing the acute Post-administration (Immediate or 1-hour) assessments, participants will hand in their ActiGraph device, they will be debriefed, and the RA will escort them back to their home. Participants will then be compensated up to \$100 (\$80 for the 4-Week visit and an additional \$20 for the last 15 of 30 daily message reports) in cash. See additional details for each measure in Table 2.

**Monthly (Online-based survey) Follow-up Assessments.** After the 4-Week *ad libitum* period of cannabis use with detailed online and in-person tracking, participants will be asked to provide monthly follow-up information. This will help track participant behavior and potential effects naturally, with a monthly self-report of marijuana use, sleep, anxiety ratings/stress management, and cognitive effects over each month, for the five additional months. All subjects will be given extensive instructions on completing the monthly message report at the Baseline Appointment and will practice answering the questions in the lab using their cell phone or a lab computer to ensure they understand the process and time commitment. They will answer online survey assessments with individually tailored links hosted by our university's licensed survey tool RedCap. To enhance the response rate, participation on monthly follow-ups will be monitored and participants will be contacted if they do not respond to one monthly survey. Participants will receive a \$6 gift card by email for every questionnaire that they complete (1st part of *Monthly follow-up survey*) a \$5 gift card by email for every TLFB that they complete (2nd part of *Monthly follow-up survey*), plus a bonus gift card of \$20 or \$15 for 5/5 or 4/5 months (1st and 2nd part) completed (\$75 or \$70 in total possible, respectively).

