#### **IV. RESEARCH STUDY DESIGN**

---

**Overview and Design of the Proposed Study.** Consistent with our preliminary study, we will recruit (from the Denver and Boulder areas): 450 participants who report a desire to use marijuana to cope with their anxiety, have had previous experience with marijuana, and report a Generalized Anxiety Disorder-7 (GAD-7) score of  $\geq 5$  (at least mild to moderate anxiety) and 75 non-using cannabis controls (matched for anxiety via GAD-7  $\geq 5$ ) who do not report an intention to use marijuana to cope with their anxiety nor any marijuana use over the prior six months. A summary of the Assessment schedule and the additional inclusion/exclusion criteria are detailed below in Table 1 and Section VI (respectively).

All participants will come to the CUChange Lab for a Baseline Appointment (Session 1) involving extensive measures of anxiety (e.g., Depression, anxiety, and stress scale, a rumination induction task, a dot probe task, rumination self-report scale, etc.) and other psychiatric symptoms, health behavior (e.g., stress, quality of life, sleep, alcohol use), the cognitive testing battery utilized in our preliminary studies, a blood draw for biomarkers of inflammation, and a motor battery (**Baseline Appointment, Session 1**). During this Baseline Appointment, a research assistant will provide information on three at-home aspects of the study: 1) the range of assigned cannabis products (e.g., differing THC to CBD ratios possible) and potential prices, 2) the ActiGraph wearable watch device that participants will be loaned to measure physical activity and sleep (during the final 2 weeks of the four week study), and 3) a microbiome collection kit that they will be given to complete (once before and once after 4 weeks of *ad libitum* use of their cannabis product). The experimental aspect of this study will be the assigned cannabis ratio, while the other aspects of this study are *ad libitum* based, with regard to the dosing schedule and choice of product type (flower or edible), by participants that would already like to use cannabis to cope with their anxiety.

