**Table 1. Schedule of Assessments.**

Visit	Duration	Includes
1. Orientation @ CINC Lab (Session 1) ASAP after phone screen [Part of Baseline Appointment]	0.5 hrs	
 
- Description of study procedures and measures
 
- Informed consent; Eligibility re-screening
 
- Strain assignment for marijuana users.
 

2. Baseline Assessment @ CINC Lab (Session 1 continued) ASAP after phone screen [Part of Baseline Appointment]	1.5 hrs	
 
- Pregnancy test, Blood Alcohol Content, Toxicology drug screen
 
- Self-report of anxiety, stress and depression (e.g., GAD-7, BAI, DASS)
 
- Rumination Induction & Dot Probe Task
 
- Questionnaires on health behavior, substance use, Psychiatric interview, and psychological measures
 
- Inflammation & cannabinoid blood draw
 
- Motor & Cognitive battery
 

3. Daily follow-up assessment for all participants 1x/day for 4 weeks (~31 days) [Between Baseline, 2-, & 4-Week Appointments]	~2 mins /day	
 
- Daily online message report on anxiety/stress management, ad libitum marijuana use (if used: amount, strain, method), and sleep; individually tailored links
 

4. 2-Week Assessment @ CINC Lab (Session 2) 2-weeks after Baseline Appointment	1hr	
 
- All Baseline measures (exception: rumination induction task removed and participant global change index added)
 
- Microbiome kit & Actigraph distributed
 

5. 4-Week Assessment @ Mobile Lab (Sessions 3 & 4) Pre (Immediately) & Post (Immediately for flower or 1 hour for edible) self-administration [4-Weeks after Baseline Appointment]	2 hrs	
 
- All Baseline measures/tasks
 
- Microbiome kit & Actigraph wearable collected
 

3. Monthly follow-up assessment for all participants 1x/month for 5 additional months [After 4-Week Appointment]	~12 mins /month	
 
- Monthly online survey; individually tailored links
 

Total time (6 months)	8 hrs	Participants paid \$335

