Rumination Induction (RI) Task	Focused breathing and rumination induction exercise to experimentally examine the active occurrence of rumination thought and how it affects stress and cognitive function.,, intermixed with a visual analog scale of perceived anxiety and stress used to measure changes in intensity of negative emotional responses (0-10; Rood et al 2012, Arch & Craske 2006).	

Perceived Discrimination Scale (PDS)	A 20-item scale to measure how often people feel that others treat them badly or unfairly based race, ethnicity, gender, age, religion, physical appearance, sexual orientation, or other characteristics separated into two subscales: The Lifetime Discrimination Scale and Daily Discrimination Scale.	
Positive and Negative Affect Schedule (PANAS)	Self-rated measurement of positive and negative affect with two 10-item scales from 1 (not at all) to 5 (very much; Watson 1988).	
Profile of Mood States (POMS)	The Profile of Mood States (POMS) will be used to collect baseline information on mood as well as information on mood changes throughout the study. (Johanson & Uhlenhuth, 1980; McNair, Lorr, & Droppleman, 1971).	
4-Week (Post-Administration) Appointment		
Assessment of Marijuana Potency	At the end of the experimental session, participants will be asked to report which product they received including the ratio and potency of THC and CBD in that strain.	
Appointments/Time points	Instruments/Procedures	Time to complete
Baseline Appointment (CINC Lab)	Informed consent & study orientation; BAC test; Urine toxicology & Pregnancy test; Physiological measures; Anxiety & Stress ratings; 1 st Blood draw; Questionnaires; Cognitive & Motor Battery; Microbiome distributed; Appointment 2 scheduling; Monetary Compensation.	120 minutes
Daily Follow-Up Messages (Days 1-15)	Respond to brief questions (online) about marijuana use, sleep quality, and anxiety/stress management 1x/per day for 2 weeks.	~2 mins/day x 15 days (~30 mins total)
2-Week Appointment (CINC Lab)	BAC test; Physiological measures; Anxiety/Stress ratings; 2 nd Blood draw; Questionnaires; Cognitive & Motor Battery; Microbiome & Wearable distributed; Appointment 3 scheduling; Monetary Compensation.	60 minutes

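### The protocol promises microbiome samples before and after assigned use, but its procedures conflict on one kit or two, so a pre-use sample is not assured

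*Combined protocol and SAP*

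**What the plan says.** Two places promise paired samples. The design overview in Section IV describes "a microbiome collection kit that they will be given to complete (once before and once after 4 weeks of" ad libitum use. The closing paragraph on the gut microbiome in Section XII states: "Gut microbiome data will be collected at two time-points during this study, once before and one after study cannabis use". The same paragraph gives the purpose: "we will examine the relationship between changes in the gut microbiome with changes in anxiety and inflammatory biomarkers in the blood".

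Three places supply one kit. The opening paragraph on microbiome collection in Section XII reads "Subjects will be given one kit during their 2-Week Appointment and will return the kit to research staff" at the 4-Week visit. The 2-Week Appointment text says "Subjects will also be given one at-home microbiome collection kit at this visit", with completion "as near as possible to their 4-Week Appointment (after using their product"). Table 1 has "Microbiome kit & Actigraph distributed" in the 2-Week row, collection in the 4-Week row, and no microbiome item in the Baseline rows.

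One place supplies two. The appointment timetable at the end of Table 2 has "Microbiome distributed; Appointment 2 scheduling" in its Baseline row and lists distribution again in its 2-Week row. Its only return step is in the 4-Week pre-administration row.

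**The concern.** An analysis of within-person change needs two samples from each participant, the first taken before the exposure of interest begins. Strain assignment and the purchase instruction come at the end of the Baseline Appointment, and participants may then buy and use the product when they like. A kit first handed out two weeks later, and meant to be filled near week 4, can only describe the state after assigned use.

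A missed pre-use stool sample cannot be collected afterwards. Section XII says the microbial DNA is mainly for banking at present. That does not soften the problem, because a later analysis can use only what was banked. The controls are also not randomised: they differ from users by design in recent cannabis use and in wanting to use it for anxiety. Without a baseline sample, pre-existing microbiome differences between users and controls cannot be separated from anything that happened during the four weeks.

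**Working it through.** No power or alpha figure is involved. The check is a count of kits out and kits back in each part of the document.

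| Place | Kits handed out | When completed | Return listed |
|---|---|---|---|
| Section IV, overview | not counted | before and after the 4 weeks | none |
| Section XII, gut microbiome, closing paragraph | not counted; two time points | before and after assigned use | none |
| Section XII, gut microbiome, opening paragraph | 1, at week 2 | not stated | week 4 |
| Section XII, 2-Week Appointment | 1, at week 2 | near week 4, after product use | date not given |
| Table 1 | week 2 only | not stated | week 4 |
| Section XII, 4-Week Appointment | none | not stated | one kit, week 4 |
| Timetable at end of Table 2 | Baseline and week 2 | not stated | one kit, week 4 |

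**If staff follow the one-kit procedure** (Section XII collection text, 2-Week text, Table 1):
- Kits out = 1, kits back = 1, pre-use samples = 0.
- Change = post-use value − pre-use value. The second term is missing for everyone, so change is undefined.
- Number affected, from the attrition paragraph in Section IV: 4 groups × 86 (three flower, one control) + 3 edible groups × 58 = 344 + 174 = 518, which the plan rounds to about 520.

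**If staff follow the Table 2 timetable:**
- Kits out = 2, kits back listed = 1.
- A pre-use sample is possible but not secured. No text requires the Baseline kit to be filled before first use of the assigned product, and the 2-Week row lists no return. A participant could fill the kit after starting the product, or never be asked for it.

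**The companion diet survey shows the same split.** The Section XII microbiome text places the EATS survey at the 2-Week and 4-Week pre-administration visits. Table 2 places it at Baseline and 4-Week pre-administration. The first timing does not cover a pre-use sample; the second does.

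**The case against.** The title to this point could be pushed further, and a reader might infer that no pre-use sample exists at all. The documents do not support that. The Table 2 timetable lists a kit at Baseline, Section XII has participants taught at Baseline how to collect and return samples, and the intent to sample before and after is stated twice. What can be said is that the instructions disagree and that none of them secures the first sample.

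A reader might also infer that without a baseline the microbiome data support only a confounded cross-sectional comparison. That goes too far as well. The three strains are randomly assigned among users, so comparing post-use samples between strains remains a randomised comparison. The loss falls on the change analysis and on users versus controls.

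Three further points stand:
- Users may already be using cannabis at entry, so a Baseline sample precedes the assigned product and not necessarily all recent exposure.
- The microbiome is absent from Aims 1-3, the power analysis and the statistical analysis plan.
- The Spring 2023 amendment refers to participants who have finished the study; new wording cannot create Baseline samples for them.

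The low stakes do not remove the conflict. Section III says the pilot could not complete a microbiome analysis and that the present study will, and Section XII commits to a change analysis. Three operational texts, followed as written, make that analysis impossible, which is more than an omitted detail.

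**Conclusion.** The point holds as a contradiction in the collection procedure with a concrete consequence. On the one-kit reading, 0 of about 520 planned recruits have a pre-use sample and the change analysis cannot be computed. On the two-kit reading, the number of usable pre-use samples is unknown, because timing and return are unspecified. The documents do not show which version staff followed, so the actual loss cannot be stated.

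The loss should not be sized by the precision that baseline adjustment would bring. That needs a within-person correlation the documents do not give, and it would not measure what is lost from relating one change to another.

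The matter is worth correcting but affects no primary conclusion, since the outcome is exploratory and outside Aims 1-3.

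**What to change.** Reconcile the following to one two-kit plan: the Section IV overview, Table 1, the Section XII microbiome, 2-Week and 4-Week texts, and the EATS entry and timetable in Table 2.

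1. Give kit 1 at the Baseline Appointment, to be completed before first use of the assigned product and returned by week 2. Add the return to the 2-Week row.
2. Give kit 2 at week 2, completed near week 4 and returned at the 4-Week visit.
3. Record the date each sample was taken and the date of first assigned use, so that a supposed pre-use sample can be verified.
4. Settle the EATS timing so that the survey accompanies both samples.
5. For participants without a verified pre-use sample, or if only one kit is intended, replace the change analysis with a comparison of post-use samples among the randomised strains, and state that users versus controls has no baseline.

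The cost is a second kit per participant where one is not already supplied, its return handling and storage, and wording changes in several sections. The two-kit intent is already in Section IV, the closing microbiome paragraph and the Table 2 timetable, so the design itself does not change. For participants who have already finished, only item 5 applies, along with any sample and first-use dates that can be recovered from existing records.
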